5.11 Rescue Therapy (aHUS only)

Plasma Transfer or Dialysis/Hemofiltration will be considered Rescue Therapy.

If Rescue Therapy is known to be required on a day during treatment, then the Rescue Therapy should be completed before any rVA576 (Coversin) is given to the subject on that day, if possible.

The following rules should be used when the Investigator administers Rescue Therapy to the subject:

Administer 60 mg rVA576 (Coversin) within 60 minutes after the end of each Rescue therapy.

- If \leq 6hrs to the next scheduled dose: 15mg of rVA576 (Coversin) at the next scheduled dose, then resume to dose subject was prior Rescue Therapy.
- If $>$ 6hrs to next scheduled dose: 30 mg of rVA576 (Coversin) at the next scheduled dose, then resume to dose subject was prior Rescue Therapy.

Examples:

Dose/time	Rescue Therapy (RT) and ablation dose	Next Dose/Time	Next Dose/Time
30 mg /9am	RT ends at 4pm then 60 mg of rVA576 (Coversin) (within 1hr after end of PT) ≤6hrs till the next scheduled dose	15mg/9pm	30mg/9am
45mg /8am	RT ends at 12pm then 60 mg of rVA576 (Coversin) (within 1hr after end of PT) >6hrs till the next scheduled dose	Evening dose 8pm 30 mg of rVA576 (Coversin)	45mg/8am

It is the responsibility of the PI to ensure that details regarding the medication, therapy, or procedure are recorded in full in the patient's source/chart and CRF.

Additional PK/PD samples may be required in case of Rescue Therapy.

5.11.1 Plasma Transfer (aHUS only)

The need for Plasma Transfer during the clinical trial should be guided by:

- a) A new decrease in platelet counts > 25% below the previous / baseline Platelet Count value and to a level less than $100 \times 10^9/L$; or
- b) A new decrease in platelet count below $40 \times 10^9/L$; or
- c) An emergent and new neurological, renal or another clinical event as prospectively defined for each patient.
- d) In the judgement of the Principal Investigator administering Plasma Transfer is required for the best interests of the subject.

If one of these conditions applies, then the Investigator may, at his or her discretion, prescribe Plasma Transfer treatment based on the clinical assessment of the subject. The investigator should inform the CRA if Plasma Transfer is required during the clinical trial.

If Plasma Transfer treatment is required, the following details need to be recorded in the subject medical records for each event:

Start and end date; Total number of sessions; Fresh Frozen Plasma volume used for each session (ml/kg/session); and Adverse reactions.

5.11.2 Dialysis / Haemofiltration

Subjects will not be generally permitted to receive new Dialysis unless there is compelling medical need, for example due to:

- a) Hypervolaemia unresponsive to diuretics
- b) Refractory electrolyte imbalance, or

- c) New-onset uraemic encephalopathy, and after discussion with the Sponsor that details regarding the medication, therapy, or procedure are recorded in full in the patient's source/chart and CRF.
- d) It is deemed necessary by the PI in the best interests of the subject

If dialysis treatment is administered, the following details need to be recorded in the subject medical records for each event: Start and end date; Serum creatinine value at the start and end of dialysis; Total number of sessions; Type of dialysis membrane used; Type of generator used; Type of dialysis; Adverse reactions

5.12 Quality of life questionnaires (EORTC QLQ C30 , EQ-5D-5L & FACIT-F)

The subject will complete the EORTC QLQ C30 (for some PNH patients only), EQ-5D-5L and FACIT-F (both PNH & aHUS) questionnaires and Sponsor non validated questionnaire at each clinic visit. The data will be transcribed to the eCRF and subsequently analysed.

EORTC is a questionnaire designed to assess (some of) the different aspects that define the QoL of (a specific group of) patients

FACIT-F (functional assessment of chronic illness therapy - fatigue) is a 13-item fatigue scale, which uses a symptom specific measure.

The EQ-5D questionnaire is made up of two components; health state description and evaluation. In the description section, health status is measured in terms of five dimensions (5D); mobility, self-care, usual activities, pain/discomfort, and anxiety/depression. Mobility dimension asks about the person's walking ability. Self-care dimension asks about the ability to wash or dress by oneself, and usual activities dimension measures performance in "work, study, housework, family or leisure activities". In pain/discomfort dimension, it asks how much pain or discomfort they have, and in anxiety/depression dimension, it asks how anxious or depressed they are. The respondents self-rate their level of severity for each dimension using a five-level (EQ-5D-5L) scale. In the evaluation part section, the respondents evaluate their overall health status using the visual analogue scale (EQ-VAS).

The Questionnaire on self-injection will be completed by the patient (this is a non-validated questionnaire).

6 Stopping Rules and Discontinuation Procedures

6.1 Termination or suspension of the study

The Sponsor may prematurely terminate or suspend the study at any time for the following reasons:

- Safety concerns e.g. occurrence of many serious ADRs
- Achieving the purpose of the study is considered impossible (e.g. inadequate recruitment of subjects)

If the study is prematurely terminated or suspended, the Sponsor should promptly inform the Investigators. The Investigator or designee should promptly inform the

participating subjects and change the study medication to other appropriate therapy(ies).

The Investigator may prematurely terminate or suspend the study at their medical institution with the agreement of the Sponsor. This may be done at any time during the study if they consider that ensuring patient safety during the study is difficult due to safety concerns (e.g., occurrence of many SAEs).

The Sponsor may prematurely terminate or suspend the study at a particular medical institution at any time during the course of the study, if major violations/deviations of the protocol or other procedures has not been improved or ICH GCP has not been followed.

If the study is prematurely terminated or suspended, the Sponsor should promptly inform the Investigators. The Investigator or designee, should promptly inform the, participating subjects and change the study medication to another appropriate therap(ies) and inform the corresponding Ethics Committees. All supplies should be returned.

Whichever party terminates the study will provide a written statement as to the reason for the termination.

The Sponsor (or CRO) will notify Regulatory Authorities as appropriate of premature terminations. The Investigator or their designee should promptly inform the corresponding Ethics Committee (EC).

6.2 Withdrawal criteria

In accordance with applicable regulations, a patient has the right to withdraw from the study at any time and for any reason, without prejudice to their future medical care by the physician or at the Institution. Should a patient withdraw from the study, then the patient will not undergo any further study-specific procedures or receive any treatment mandated by the protocol.

If a subject fails to attend scheduled trial assessments, the Investigator must determine the reasons and the circumstances as completely and accurately as possible.

In the event of the premature withdrawal of a patient from the trial, the end of trial visit should be carried out as completely as possible. Minimally, a safety assessment should be performed.

In the case of withdrawal due to the occurrence of unacceptable toxicity, the patient will be requested to remain under the supervision of the Investigator until the toxicity has resolved or is no longer considered to be clinically significant by the Investigator.

If an Adverse Event classified as severe results in patient withdrawal from the study, the subject will be followed until the AE (or SAE) resolves or stabilises, and any interventions required to resolve or stabilise the event will be recorded in the eCRF.

All withdrawals must be documented in the eCRF. A patient may be withdrawn in any of the following circumstances.

- Withdrawal of consent (mandatory withdrawal)
- Intake of non-permitted concomitant medication (may be discussed with the Sponsor and dependent on the nature of the medication)
- Patient is non-compliant with more than three consecutive missed doses and two missed clinic visits, in the opinion of the Investigator (discretionary withdrawal)
- If discontinuation is considered necessary by the Investigator and/or Sponsor (mandatory withdrawal)
- Request of Regulatory Agency (mandatory withdrawal)
- Patient develops an illness that would compromise his participation in the study (may be discussed with sponsor)
- Patient is not achieving complete inhibition at the maximum assigned dose (inadequate response to rVA576 (Coversin) treatment)
- Pregnancy, unless the patient wishes to consent to a termination.

6.3 Accountability procedures

In accordance with GCP, the clinical unit will account for all study medication. The clinical unit are responsible for study medication accountability, reconciliation, and record maintenance.

Drug accountability records will be maintained during the study as follows:

- Amount of study medication received from the Sponsor
- Amount distributed to each patient and returned by them
- Amount of unused drug returned to the Sponsor or destroyed at Sponsor's request.

In addition, in the event of necessary disposal of opened but wasted medication, the disposal should be documented appropriately (i.e. witnessed) in accordance with applicable local regulations, and GCP procedures.

Patients are required to return used and expired vials to the clinical unit and report to the site the number of unused vials remaining in their fridge. Storage bags will be provided to each patient. For all unused study medication, the patient should adhere to the storage instructions until the study medication is returned to the clinical unit.

If for any reason a site cannot dispose of used vials at site due to local policy, then they need to inform the Sponsor immediately.

6.4 Compliance

Reasonable levels of compliance are assumed as a condition of entry (prior enrolment in and completion of a rVA576 (Coversin) clinical trial). As a measure of compliance, all empty rVA576 (Coversin) vials will be returned to the clinical unit and diary cards

will be reviewed by research staff. At the end of the study, all unused vials will be returned to the Sponsor or representative or destroyed at site.

In addition to the above measures, clinic staff may call the patient's home or set up an automated text message reminder according to the subjects dosing schedule.

Example text as follows: "A gentle reminder - please administer your medicine this morning/evening and record the time, dose and location of injection in the Patient Dosing Diary.

6.5 Interruption of Treatment

If treatment is interrupted, either for reasons outside the patient's or the investigator's control or because it is considered to be in the patient's best interest it may be resumed at the discretion of the investigator and Sponsor. Any interruption of >24 hours will require an ablating regimen of 60mg followed by 30mg 12 hours later before resuming normal dosing, this should be discussed with the Sponsor. In the event of an interruption of treatment of >28 days, the investigator should discuss with the Sponsor the advisability of resuming treatment.

7 Safety Reporting

All AEs occurring from the signing of the voluntary Informed Consent Form (ICF) to the end of the trial visit will be recorded. All adverse events, whether or not considered to be related to the study drug, will be monitored and reported at all stages of the study. Adverse events occurring between clinic visits will be reported by the patient or recorded at the next clinic visit and entered on the adverse event form of the case report forms. All adverse events must be fully recorded in the patient notes throughout the entire study period and will be transcribed into the subject's eCRF.

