5.5 Measurements conducted on blood draws

5.5.1 CH50 assay

It appears that in PNH and aHUS, close to 100% inhibition of CH50 activity is necessary for clinical control of the disease. Serum CH50 assay is currently the most sensitive and quickest means of detecting inadequate control during anti-complement therapy as other indicators, such as LDH lag 24 - 48 hours behind the change in CH50. In practice, the Quidel ELISA assay, which is used to measure complement activity in units of CH50 U Eq/mL has a lower limit of quantification (LLOQ) of 10 CH50 U Eq/mL with individual normal baseline values ranging from 58-156 CH50 U Eq/mL. Thus the assay is insensitive to differences in CH50 when there is <10 CH50 U Eq/mL residual complement activity. Therefore, for practical purposes, the Central Laboratory (which will conduct all CH50 assays during the trial) considers values less than 10 CH50 U Eq/mL as completely inhibited. In previous trials (AK577, AK578 and AK579) with rVA576 (Coversin) the LLOQ of the CH50 was 8 CH50 EU/mL. The LLOQ has increased because the assay is now being performed using an automated system for the ELISA.

CH50 samples will be collected as per Schedule of Events.

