5.10 Missed doses

For PNH patients:

For a missed dose of more than >24 hours, the sample for PD (CH50) analysis should be taken if possible just prior to the next morning dose of rVA576 (Coversin). As the CH50 results will not be available for some days the Investigator should be guided by the history, clinical signs or platelet count and LDH. In some cases, the PI may feel that an ablating dose is not required and the patient should resume their usual dosing schedule as soon as possible. In PNH, clinical signs of intravascular haemolysis following resumption of dosing mandates re-initiation of the AD schedule. The CRO and the Sponsor should be informed as soon as possible.

Dose	Interval	Missed Dose <4hr	Missed Dose <24hrs	Missed dose by day(s)>24hrs
15mg	12 hourly	Dose to be taken as soon as patient realizes	Take 15mg dose immediately and 15mg dose at usual time	Take ablating dose 60mg/30mg. then take dose as per usual routine
22.5mg	12 hourly		Take 22.5mg dose immediately and 22.5 mg dose at usual time	
30mg	12 hourly		Take 30mg dose immediately and 30mg dose at usual time	
30mg	24 hourly		Take 45mg dose immediately and 45mg dose at usual time	
45mg	24 hourly		Take 45mg dose immediately and 45mg dose at usual time	

For aHUS patients:

In the event of one missed dose (defined as a dose not taken within a one-hour time window either side of the specified time) the following procedure should be adopted by the patient:

- Take the appropriate dose as per the day of the protocol as soon as possible and then resume the usual dosing schedule at the specified times

In the event of more than one missed dose the CRO and the Investigator's clinic should be informed as soon as possible and the following procedure should be adopted:

- Take 60 mg Coversin followed by 30 mg 12 hours later and then resume the usual dosing schedule (i.e. between 07:00 and 11:00 hrs daily) at the first time point after the ablation doses.

The Investigator's clinical staff should arrange for a Central laboratory blood draw for PK/PD to be taken 3 days \pm 1 day after first becoming aware of the missed doses in this situation.

The sample for PD (CH50) analysis should be taken just prior to dosing with rVA576 (Coversin).

As the CH50 results are unlikely to be available for some days the Investigator should be guided by the history, clinical signs or platelet count and LDH as to whether it is necessary to administer additional Ablating Doses.

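### For a PNH lapse of more than 24 hours that meets both sections, 6.5 requires the ablating regimen while 5.10 lets the PI omit it; separately, 7.2.3 can be read to count that regimen as an overdose

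*Protocol*

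**What the plan says.** Protocol 6.5 opens with treatment that is interrupted "either for reasons outside the patient's or the investigator's control" or because stopping is thought best for the patient. Resumption is at the discretion of the investigator and the Sponsor. It then sets the restart rule: "Any interruption of >24 hours will require an ablating regimen of 60mg followed by 30mg 12 hours later before resuming normal dosing", and adds "this should be discussed with the Sponsor". The rule is not limited to one disease.

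Protocol 5.10, in its PNH part, has a text and a table. The text begins: "For a missed dose of more than >24 hours, the sample for PD (CH50) analysis should be taken if possible". Because CH50 results take some days, "the Investigator should be guided by the history, clinical signs or platelet count and LDH". It then allows an exception: "In some cases, the PI may feel that an ablating dose is not required and the patient should resume their usual dosing schedule". If signs of haemolysis appear once dosing has restarted, the ablating schedule becomes mandatory. The paragraph ends by asking that the CRO and the Sponsor be told promptly. The table entry for a miss of more than 24 hours shows no exception: "Take ablating dose 60mg/30mg. then take dose as per usual routine".

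Protocol 7.2.3 sets the overdose threshold at 90 mg in 24 hours and requires every overdose, with or without symptoms, to be reported as an AE.

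**The concern.** A supply failure lasting more than 24 hours is outside the patient's control, so it falls under 6.5. It also leaves a PNH patient with a dose missed by more than 24 hours, so it fits the 5.10 trigger, which names no cause. For that one event, 6.5 makes the regimen obligatory and brings the Sponsor in, while the 5.10 text lets the PI decide alone to omit it and only inform the Sponsor. Neither section defines its term against the other, refers to the other or says which prevails.

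At stake is a consistent restart rule after loss of drug cover. Protocol 5.5.1 says it appears that "close to 100% inhibition of CH50 activity is necessary for clinical control of the disease", and the PI makes the restart decision before the CH50 result is back. A PI who follows 5.10 in good faith for such a lapse departs from 6.5.

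A second matter concerns AE recording. The regimen's total equals the 7.2.3 threshold, so dosing that the protocol itself directs can be recorded as an overdose AE. AEs are part of the primary endpoint (Protocol 3.2.1; SAP 2.4.1).

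**Working it through.** The plan states no figure to reproduce on this point. The check compares the two rules and then does simple dose arithmetic.

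**Step 1: the two rules for PNH.**

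| | 6.5 | 5.10 text (PNH) | 5.10 table (PNH) |
|---|---|---|---|
| Event | Interruption, external cause or patient's interest | Missed dose, no cause named | Missed dose, no cause named |
| Threshold | More than 24 h | More than 24 h | More than 24 h |
| Regimen | 60 mg, then 30 mg 12 h later | Same regimen, but the PI may omit it | 60 mg/30 mg |
| Sponsor | Discuss | Inform | Not mentioned |

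The default agrees in all three columns. The difference is confined to the exception in the 5.10 text. The conflict therefore needs three things together: a PNH patient, a lapse that meets both descriptions, and a PI who uses the exception.

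**Step 2: the clock.** The nominal threshold is the same, but neither section says when the 24 hours start. Take a patient on 24-hourly dosing whose dose is 10 h late. Counted from the due time, the delay is 10 h, which is under 24 h. Counted from the last dose taken, the gap is 24 + 10 = 34 h, which is over 24 h. A reader could apply the first count in 5.10 and the second in 6.5. Any reconciling text has to fix the starting point.

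**Step 3: dose arithmetic.** Inputs are the regimen (6.5), the five PNH dosing rows (5.10 table) and the 90 mg threshold (7.2.3).

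- Ablating regimen: 60 + 30 = 90 mg within 12 h. Distance to threshold: 90 − 90 = 0 mg, so the threshold is met.
- 15 mg 12-hourly: 15 × 2 = 30 mg, which is 60 mg below.
- 22.5 mg 12-hourly: 22.5 × 2 = 45 mg, which is 45 mg below.
- 30 mg 12-hourly: 30 × 2 = 60 mg, which is 30 mg below.
- 30 mg 24-hourly: 30 × 1 = 30 mg, which is 60 mg below.
- 45 mg 24-hourly: 45 × 1 = 45 mg, which is 45 mg below.

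These amounts describe the regimens and do not measure risk. They show that, on a 24-hour-total reading, each ablating course meets the overdose definition and no usual PNH schedule does.

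**Step 4: where the AE goes.** SAP 3.4.3 treats all AEs recorded under AK581 as treatment-emergent, and SAP 4.12.1 tabulates them. An overdose record made only because the protocol was followed would therefore enter the primary safety summaries. This does not depend on the 5.10/6.5 conflict. It arises whenever the regimen is given, including with a dose increase (Protocol 5.2) or under the 5.10 table default.

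**The case against.** The strongest reply is that the two sections deal with different events. The PNH table in 5.10 speaks, in its column for short delays, of the patient noticing the miss, which suggests an individual forgetting a dose. Section 6.5 sits among the stopping rules and deals with external or medical interruptions. On that reading a supply failure belongs only to 6.5. This is a sensible reading, and it is the one the fix should write down. But the protocol does not state it: the 5.10 trigger is not limited by cause, and nothing stops a PI from applying its exception to an interruption.

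It can also be said that the practical gap is small. That stands. Both sections default to the same regimen, 5.10 asks for a CH50 sample where possible and requires the ablating schedule if haemolysis follows, and the Sponsor hears of the event either way. The Sponsor discussion in 6.5 could be seen as softening its rule, but it adds a consultation step and does not let the PI omit the regimen alone.

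A reader might infer that the sections conflict for every PNH dose missed by more than 24 hours, and that PI discretion should be withdrawn throughout. The documents do not support this. An ordinary forgotten dose does not meet the opening of 6.5, so 5.10 alone applies and its exception is a legitimate choice.

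**Conclusion.** There is a real but minor conflict in an operative dosing rule, confined to PNH lapses that meet both sections and in which the PI uses the 5.10 exception. The number of patients affected cannot be stated, because the documents give no frequency of such lapses. PNH is the population that matters, since SAP section 1 says no aHUS patients will enter.

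A reader might go further and conclude that omitting the regimen is unsafe. The documents do not show this: the 5.5.1 statement on CH50 is itself tentative, and 5.10 has a haemolysis backstop. Nor does the conflict alter any planned analysis.

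The 7.2.3 point stands on its own. It assumes that the definition is read as a 24-hour total, which is the natural reading. On it, each protocol-directed course of 90 mg adds one overdose AE to the primary safety endpoint. The number of such courses is likewise not given.

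**What to change.** Make three wording changes by amendment.

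1. In 5.10 (PNH) and 6.5, with a cross-reference each way, state that 6.5 governs any interruption meeting its opening sentence, and that for these the 5.10 exception may be used only after discussion with the Sponsor and with the reason recorded. Leave PI discretion for ordinary missed doses, and the aHUS rule in 5.10, as they are.
2. In both places, state that the 24 hours are counted from the time the first missed dose was due.
3. In 7.2.3, state that an ablating regimen of 60 mg followed by 30 mg, given as the protocol directs, is not an overdose and is not reported as an overdose AE. Any untoward event after the regimen would still be recorded under the general AE rules in 7.2.1.

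The cost is amendment text in 5.10, 6.5 and 7.2.3, and a Sponsor contact before omission in the few cases covered by the first change. No visits, samples or analyses are added.
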